**Progress Report**

## **UCI Progress**

**Please provide a detailed description of the progress of the study, including a brief summary of any interim findings or trends, and plans for the next approval period:**

Our phase 2 clinical trial has concluded recruitment, enrollment and treatment. The plan for the next approval period is to complete post treatment assessments and data analysis. Interim data was reviewed confidentially by the DSMB at their meeting in November 2023 and approved. The DSMB Meeting report was uploaded to the attachment section. Subject status breakdown: Aim 1: 168 assessed for eligibility; 106 were ineligible, 62 were randomized to study; 54 received intervention per protocol and completed all assessments, 1 withdrew from treatment but completed assessments, 4 withdrew consent from study, 2 were removed by physician; 1 is ongoing for final assessment; Aim 3: 23 assessed for eligibility; 13 were ineligible, 10 were randomized to study; 8 received intervention per protocol and completed all assessments, 0 withdrew from treatment but completed assessments, 0 withdrew consent from study, 0 were removed by physician; 2 are ongoing for final assessment. Aims 1 and 3 were the only 2 aims that were enrolling subjects and have closed enrollment. Clinicaltrials.gov has been updated to reflect close of enrollment.

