We performed a long-term study to assess the safety and potential of BCI-FES therapy. Nine chronic stroke subjects (>6 months post-ictus) with gait impairment due to foot-drop underwent 12 sessions of BCI-FES therapy (3 sessions/week, for 4 weeks). The primary outcome measure was gait velocity. Secondary outcomes were dorsiflexion active range of motion (AROM), leg motor Fugl-Meyer score, gait endurance (6-min walk test), and fall frequency. These outcomes were assessed before, on a weekly basis, and 1 month after completion of the BCI-FES therapy (Fig. 3). No subjects experienced a significant decrement in any outcome measure and there were no adverse events, indicating that BCI-FES therapy is safe. In post-hoc analysis, 6 out of 9 (66.7%) subjects had a significant improvement in gait velocity at 1 month post-therapy (average increase of 51%, or  $0.21 \pm 0.15$  m/s). While no spatial cortical reorganization was observed in any subject at the end of therapy, the Cz channel (electrode over the foot motor area) exhibited an increase in alpha- and beta-band event-related desynchronization/synchronization (ERD/ERS) magnitude in 5 of these 6 (83.3%) subjects. Conversely, these EEG changes did not occur in the 3 subjects with no gait velocity improvement. This suggests the existence of a neural process underlying gait velocity improvements. Subjects with low gait velocity (<0.4 m/s) and poor dorsiflexion AROM (<5 degrees) at baseline were 150% more likely than those with moderate-to-high gait velocity (>0.4 m/s) or good-to-excellent AROM (>5 degree) to experience an increase in gait velocity. This highlights a potential promise of BCI-FES therapy in that it may be accessible and beneficial to stroke survivors whose baseline motor functions are too low for current or emerging interventions.

Describe the primary outcome variable(s), secondary outcome variables, and predictors and/or comparison groups as appropriate for the stated study objectives/specific aims:

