Aim 1: The primary outcome measure will be gait velocity, which is directly linked to disability and social re-integration after stroke. Gait velocity will be assessed by measuring the time to traverse the middle 6 m of a 10-m walkway (5 repetitions/assessment). Secondary outcomes include: 1. Gait endurance: The distance walked over 6 minutes. 2. Fall Frequency: Number of falls experienced weekly. 3. Leg Motor Fugl-Meyer (FM) Score: Assessed according to the FM rating system. 4. Dorsiflexion Active Range of Motion (AROM) and torque: The paretic foot will be placed in an articulated brace which maintains the ankle at neutral during idling, while fixing the tibia perpendicular to the ground and the femur horizontal to the ground. The brace will be instrumented with an electro-goniometer and torque meter to automatically measure the maximum dorsiflexion AROM and torque (over 3 trials). 5. EEG Map: Subjects will undergo 64-channel EEG recording as they engage in 100 alternating 10-s long epochs of idling and attempted dorsiflexion. The EEG ERD/ERS, defined as the drop/rise in alpha (8-12 Hz) and beta (13-30 Hz) band power during attempted dorsiflexion (compared to idling), will be calculated and averaged over all epochs and across all channels. A pre-intervention baseline for each outcome will first be established. Subsequently, measurements will be performed at 1 week intervals during the intervention phase (total of 3), immediately after the intervention phase, as well as 1 and 3 months after completion of interventions. The primary efficacy outcome and endpoint will be gait velocity immediately after the intervention phase. Aim 2 (subgroup analysis of Phase II clinical trial) Since stroke is a heterogeneous disease, responsiveness to rehabilitation therapy is not uniform across all subpopulations. Hence, it is important to ensure that any new therapy, e.g. BCI-FES therapy, is matched to subpopulations that will benefit the most. The following set of baseline characteristics will be assessed during the pre-intervention phase (Fig. 6, Phase 2) for Groups 1 and 2 to determine which features influence responsiveness to BCI-FES therapy: 1. Baseline gait velocity, dorsiflexion AROM and torque: Baseline gait velocity and dorsiflexion AROM and torque will be taken from Aim 1. 2. TA volitional electromyogram (EMG): TA EMG will be assessed by having subjects attempt dorsiflexion while seated with tibia perpendicular to ground. EMG will be acquired by a bioamplifier with surface electrodes placed over the TA muscle. Subjects will be categorized as either

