#### **Statistical Considerations**

Is a statistical analysis plan appropriate for this qualitative study design?

Yes

Describe the statistical methods for the stated specific aims and hypotheses. Your analysis plans should match the stated study specific aims and hypotheses:

Aim 1: The study design is a parallel randomized controlled trial with two arms: BCI-FES dorsiflexion therapy and dose-matched conventional physical therapy. A total of 80 subjects (which includes 10% attrition) will be randomized with 1:1 ratio into the two study arms. The primary outcome is gait velocity and the secondary outcomes are gait endurance, fall frequency, leg motor FM score, and dorsiflexion AROM and torque. Outcomes measures will be evaluated at baseline, weekly during therapy, immediately post-intervention, and 1- month and 3-months post-therapy. The primary efficacy analysis (with intent-to-treat analysis with respect to treatment randomized) will be based on a linear mixed model (LMM) with gait velocity measured at baseline weeks 1-4 (time 0, 1, 2, 3, and 4) with time, treatment group and group by time interaction assess the difference in the rates of change (improvement) in gait velocity between treatment groups. Model estimation will be based on restricted maximum likelihood (REML) with unstructured covariance among repeated measurements over time. The LMM will also be applied to evaluate group difference for secondary outcomes and secondary endpoints at 1- and 3-months post-therapy. In order to determine if  $\mu$  and  $\beta$  ERD/ERS significantly changes over the 4 weeks of therapy, the ERD and ERS magnitude will be calculated for each EEG channel across all attempted dorsiflexion epochs, and for each assessment. The Mann-Whitney U test will be used to determine if any significant changes in the magnitude of ERD/ERS at each assessment with respect to the baseline. Based on the findings, each subject will be categorized as demonstrating significant changes in ERD/ERS or not. Next, all subjects will also be categorized on whether they experienced a detectable increase in gait velocity (defined as an increase in gait velocity of  $>0.16$  m/s with respect to baseline). A Chi-square test will be used to assess if there is a difference between the proportion of those with changes in ERD/ERS magnitude in those who had gait improvement within the BCI- FES therapy group. This will also be repeated for the control group. In addition, to determine if the presence of significant ERD/ERS changes was affected by group, the Chi-square test will be repeated by using BCI-FES group as the observation and the control group as the expected values. Aim 2: Data from Aim 1 will be used for analysis in this aim. The primary outcome is gait velocity immediately post-BCI-FES therapy, and the secondary outcomes are the same as in Aim 1. To test whether specific stroke features (e.g. baseline gait velocity, dorsiflexion AROM, etc.) modify response to treatment over

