**Power Analysis:** For Aims 1 and 2, the power analysis was based on a LMM with two treatment groups and 5 repeated measures (baseline and after weeks 1-4) with a significance level of 0.05. Previous studies have examined the clinically meaningful gait improvement (minimal clinically important difference) of 0.16 m/s, including a multicenter randomized clinical trial that includes conventional physical therapy. Thus, to ensure clinically meaningful effect size, we assume conventional therapy will have an improvement of 0.25 m/s after 4 weeks of treatment. Data from prior studies as well as our own preliminary data (n=9) found that the between-subject variance in gait velocity of about 0.16 m/s and the within-subject correlation of about 0.95. Table 1 below shows the power to detect improvement of BCI-FES over conventional therapy of 30% - 40%. Thus, for the proposed study with n=80 patients (40 per arm) has 92% to 94% power to detect an effect size/improvement of 35% for various between-subject variance (0.15 m/s to 0.17 m/s) in determining treatment efficacy (Aim 1). We note that n=80 total has been intentionally inflated in order to accommodate the objectives of aim 2 to examine modifying factors, such as TA MEP (primary modifying factor), on treatment. That is, for n=30 per arm the power to determine efficacy (aim 1) is 85% for detecting an effect size/improvement of 35% (between-subject variance 0.16 m/s); thus, increasing to n=40 allows for detecting modifying factor on treatment (aim 2) when the interaction effect smaller (effect size 28% can be detected with 79% power). Table 1: Power to detect improvement in gait velocity due to BCI-FES over conventional therapy for n=80 with various between-subject variance (aim 1). Between-Subject Variance Effect Size (Improvement) 0.15 0.16 0.17 30% 87.3% 85.2 % 83.0% 35% 94.5% 93.5% 92.1% 40% 98.3% 97.7% 97.0% Aim 3: Total sample size of n=20 will have 82% power to detect an R-square of 0.16 (attributed to the effect of interest, e.g., w x group) adjusted for baseline measurement and main effects whose total contribution R-square is 0.5 (for 3 independent variables) in a multiple regression model.

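### The between-arm chi-square for ERD/ERS change treats the control arm's counts as fixed expected values, so at an assumed 5% level its type I error is about 16-19% with equal arms

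*Combined protocol and SAP*

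**What the plan says.** The relevant text is the last part of the Aim 1 analysis in Statistical Considerations. ERD/ERS magnitude at each assessment is tested against baseline within each subject, after which "each subject will be categorized as demonstrating significant changes in ERD/ERS or not". Chi-square tests then relate this status to gait improvement within the BCI-FES arm and, separately, within the control arm.

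A further test is added "to determine if the presence of significant ERD/ERS changes was affected by group". Its method is given in the same sentence: "the Chi-square test will be repeated by using BCI-FES group as the observation and the control group as the expected values".

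The arms being compared are randomized: "A total of 80 subjects (which includes 10% attrition) will be randomized with 1:1 ratio into the two study arms". No significance level is given for this test. The only one stated is in the power analysis for the linear mixed model (LMM), "with a significance level of 0.05". Nothing elsewhere in the document restates or corrects the comparison.

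**The concern.** Whether ERD/ERS change depends on arm is a two-sample question, and both arms' counts are random. The sentence makes one arm the observed counts and the other the expected counts. In an ordinary 2x2 chi-square the expected counts come from the pooled margins, never from one arm. As written, the test asks whether the BCI-FES counts fit a fixed distribution that happens to be whatever the controls showed.

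There are two consequences:

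- The test rejects far too often when there is no arm effect.
- The statistic has a zero denominator, and is undefined, if no controls or all controls are flagged.

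This is the plan's only between-arm test of the binary ERD/ERS-change status. The Aim 1 hypothesis appeals to neural repair mechanisms, so a spurious arm difference here could be read as support for it.

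**Working it through.** The documents give no type I error or power for this test, so there is no stated figure to reproduce.

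**Inputs**

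- Allocation 1:1, 40 per arm planned (Statistical Considerations).
- 36 per arm after the stated 10% attrition: 40 × 0.9 = 36.
- 31 per arm as an even split of the Aim 1 total in the Progress Report, "62 were randomized to study". The report does not give the split by arm, so 31:31 is an assumption.
- 27 per arm, close to an even split of those with completed assessments: 54 + 1 = 55, with one more still ongoing.
- Alpha two-sided 5%, assumed for this test; critical value 3.841 on 1 df.
- Pilot rate of ERD/ERS change 5/9: 5 of the 6 subjects who improved, and none of the rest, since "these EEG changes did not occur in the 3 subjects with no gait velocity improvement".

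**Large-sample size of the test**

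Under the null with n per arm and common proportion p, Var(p1 − p2) = 2p(1 − p)/n. The test as written uses p(1 − p)/n. The statistic therefore behaves like twice a chi-square on 1 df:

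P(reject) = P(|Z| > 1.96/√2) = P(|Z| > 1.386) = 0.166.

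For n1 BCI-FES and n2 control subjects this becomes P(|Z| > 1.96/√(1 + n1/n2)).

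**Exact size**

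Both binomials were enumerated in full for p = 0.20 to 0.80 in steps of 0.05. With a of n1 flagged on BCI-FES and b of n2 on control, E1 = n1·b/n2 and E0 = n1 − E1, and

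X² = (a − E1)²/E1 + (n1 − a − E0)²/E0.

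Undefined tables were counted as non-rejections; at 31-40 per arm their probability is at most 0.1% over this range.

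| BCI-FES : control | As written | At p = 5/9 |
|---|---|---|
| 40 : 40 | 15.5-18.0% | 16.0% |
| 36 : 36 | 17.2-19.5% | 19.2% |
| 31 : 31 | 16.5-17.7% | 16.7% |
| 27 : 27 | 16.8-18.9% | 16.8% |
| 27 : 35 (assumed split) | 14.7-15.6% | 15.3% |
| 35 : 27 (assumed split) | 21.0-22.1% | 21.3% |

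The large-sample formula gives 14.1% for 27:35 and 19.6% for 35:27. An ordinary 2x2 Pearson chi-square, enumerated in the same way, gives 4.5-5.7% at 31, 36 and 40 per arm and for both uneven splits, and 4.2-5.7% at 27.

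**Worked example, 40 per arm, 28 flagged on BCI-FES and 21 on control**

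- As written: X² = 7²/21 + 7²/19 = 2.33 + 2.58 = 4.91, p = 0.027.
- 2x2 chi-square: pooled proportion 49/80 = 0.6125; X² = (7/40)²/[0.6125 × 0.3875 × 2/40] = 2.58, p = 0.108.
- Fisher's exact: p = 0.168.

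**Undefined statistic**

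If the true proportion were 0.05 (an assumption), the chance that no control is flagged is 0.95^40 = 12.9% at 40 per arm and 0.95^31 = 20.4% at 31.

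**The case against.** The strongest reply is that an ordinary 2x2 test was probably meant. That may be so, but the sentence assigns the observed and expected roles to particular arms, and nothing else in the plan overrides it. An analyst who follows it runs the wrong test; one who does not departs from the plan.

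The second reply is that the error rate depends on how the sentence is read and on how many subjects are flagged. Both points are fair:

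- Because the test is described as repeated, it could mean the four-cell table of ERD/ERS change by gait improvement. That reading is worse: about 27% in large samples and 31-33% at 31-40 per arm.
- The flag is built from many channels, and the plan gives no multiplicity rule for it, so nearly everyone might be flagged. At a true rate of 0.95 the error falls to about 7-12% for 27-40 per arm, still above 5%. At 0.98 it is 0.6-2.1%, but only because the statistic is then undefined in 45-58% of trials. The pilot 5/9 comes from nine subjects and the Cz channel, so it is weak evidence about the rate to expect here.
- A continuity correction brings the rate down only to about 8-16%.

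The third reply is that little hangs on this test, and that stands. The primary analysis is the gait-velocity LMM, and mechanism is assigned to Aim 3. A valid between-arm LMM of ERD/ERS magnitude is arguably planned too: the outcome definitions in Background and in Study Design list the EEG map as a secondary outcome, with magnitudes that "will be calculated and averaged over all epochs and across all channels". The list of secondary outcomes in Statistical Considerations leaves EEG out, however, and such a model would not repair the binary test.

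**Conclusion.** The concern holds. The comparison is wrong as written, not merely short of detail. With equal arms, a nominal 5% level and the two-cell reading, the test would declare an arm effect that does not exist about one time in six: 16.6% in large samples, and 15.5-19.5% exactly across 27 to 40 per arm for true flag rates between 0.2 and 0.8.

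These rates rest on an assumed alpha, on an assumed even split of the subjects actually randomized, and on a flag rate that is not extreme. The neglect of control-arm sampling error depends on none of these. Because the damage is confined to a supporting EEG analysis, this should be fixed but does not threaten the primary conclusion.

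**What to change.** Replace the sentence with a two-sample comparison of independent proportions: a 2x2 chi-square or Fisher's exact test of ERD/ERS-change status by arm, or equivalently a logistic regression of that status on arm. Report the risk difference with its 95% CI, and state the alpha for this analysis.

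The cost is one sentence in the analysis plan. The data, conduct and sample size do not change. The Progress Report places data analysis in the next approval period, so the correction should be documented before the ERD/ERS comparison is run.

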#### Background & Purpose of the Research

Describe the purpose, specific aims or objectives and specify the hypotheses or research questions to be studied:

Aim 1: Quantify the neurological and functional improvements due to BCI-FES dorsiflexion therapy compared to dose- and intensity-matched conventional therapy. Hypothesis: The neural repair mechanisms underlying BCI-FES dorsiflexion therapy will lead to improvements in neurological and functional outcomes that are greater and longer-lasting than those achieved by dose-matched conventional therapy. Aim 2: Identify stroke features that are linked to responsiveness to BCI-FES dorsiflexion therapy. Hypothesis: Based on preliminary studies, baseline gait velocity, dorsiflexion AROM/torque, TA muscle electromyogram (EMG) and motor evoked potentials, the magnitude of EEG alpha- and beta-band ERD/ERS during attempted dorsiflexion, and sensory function will influence the response to BCI-FES dorsiflexion therapy. Aim 3: Investigate the mechanism of action of BCI-FES dorsiflexion therapy. Hypothesis: BCI-FES therapy reinforces the connectivity between foot M1 and the  $\alpha$ -MN due to Hebbian plasticity. The study will have a significant impact in rehabilitative neuroscience, clinical neurorehabilitation,

Provide the scientific or scholarly rationale for the research and describe the relevant background information and the specific gaps in current knowledge that this study intends to address:

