
treatment duration, a LMM model with three-way interaction (group, time, modifying factor) will be used to test whether the slope of the three-factor interaction is zero (specific stroke feature does not modify response to treatment). Aim 3: The aim is designed as a randomized controlled study with two arms: BCI-FES dorsiflexion therapy and BCI-robotic orthosis therapy. A total of 20 subjects will be recruited and randomized with 1:1 ratio into the two arms. The primary outcome is gait velocity, and the secondary outcomes are ankle torque and active range of motion. The main interest is to evaluate if the correlation between  $M1 \rightarrow \text{EMG}$ ,  $w$ , (normalized range: 0-1), and gait velocity is different between the two study groups averaged over time after treatment, adjusted for baseline outcome measure. For example, with outcome gait velocity, the analysis will be based on a regression model with group,  $w$ , and their interaction, adjusted for baseline gait velocity. The relationship between both  $w$  with secondary outcomes will be similarly analyzed.

Describe the statistical method(s) that will be used to analyze the primary outcome(s) or endpoints:

The primary statistical methods for primary outcome, gait velocity, is already described in Aim 1 above.

If appropriate describe secondary or post hoc analyses of primary outcome(s) or other exploratory analysis and if necessary, provide a breakdown of the methods used per outcome or endpoint:

The statistical method for secondary outcome measures is similar to the primary outcome, and is already described in Aim 1 and 2 above.

**Sample Size Determination:** Explain how the overall target sample size was determined (e.g., power analysis; precision estimation), providing justification of the effect size for the primary outcome based on preliminary data, current knowledge/literature and/or cost consideration; if appropriate, provide sample size justification for secondary outcomes. Power analysis should (at least) match the primary outcome/endpoint:

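### Aim 2 tests about six to eight candidate response features on gait velocity with no error control, and its primary modifier is not carried into the analysis plan

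*Combined protocol and SAP*

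**What the plan says.** All references are to the combined protocol and SAP.

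- **Purpose.** Background & Purpose of the Research states Aim 2 as: "Identify stroke features that are linked to responsiveness to BCI-FES dorsiflexion therapy". The hypothesis names "baseline gait velocity, dorsiflexion AROM/torque, TA muscle electromyogram (EMG) and motor evoked potentials, the magnitude of EEG alpha- and beta-band ERD/ERS during attempted dorsiflexion", and adds that "sensory function will influence the response to BCI-FES dorsiflexion therapy".
- **Outcomes.** Statistical Considerations, Aim 2: "The primary outcome is gait velocity immediately post-BCI-FES therapy, and the secondary outcomes are the same as in Aim 1". Aim 1 lists five secondary outcomes there: gait endurance, falls, leg motor Fugl-Meyer score, dorsiflexion AROM and torque. The secondary-outcome method is described as similar to the primary one.
- **Test.** "a LMM model with three-way interaction (group, time, modifying factor) will be used to test whether the slope of the three-factor interaction is zero". The modifying factor is in the singular, and the examples of stroke features are left open-ended.
- **Level.** The only level given for Aims 1 and 2 is in the power analysis: "with a significance level of 0.05".
- **Primary modifier.** The power analysis says that the sample was enlarged to "examine modifying factors, such as TA MEP (primary modifying factor), on treatment". The Aim 2 analysis text does not mention this ranking.
- **Operational feature list.** The numbered Aim 2 list under Study Design covers baseline gait velocity, AROM and torque, volitional TA EMG, EEG features in two bands, and the Nottingham sensory score. MEP is not on it.
- **Who can have an MEP.** The TMS items in the exclusion criteria rule out TMS for several groups, including people with a past cortical stroke, epilepsy or neurosurgery. These people stay in the main study.

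No section adjusts the Aim 2 tests for multiplicity, says when a feature counts as identified, or calls the aim exploratory.

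**The concern.** Aim 2 is meant to produce a list of features for matching patients to the therapy. Each feature gets its own interaction test, and nothing limits the chance that at least one is significant by luck. The primary-modifier label would give one protected test, but it appears only in the sample-size reasoning. It is missing both from the analysis text and from the list of features to be measured for this aim. An analyst following the plan could report any significant interaction as a feature of response, and a reader could not tell a planned primary result from the best of several.

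The Aim 1 efficacy conclusion is not affected.

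**Working it through.** **Inputs**

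- Level per test: 0.05, from the power analysis. Applying it to each Aim 2 test is an inference. Sidedness is not stated; two-sided reproduces the plan's power figures and one-sided does not.
- Features: the hypothesis gives 8 if AROM and torque are split and alpha and beta ERD/ERS are split (gait velocity, AROM, torque, EMG, MEP, alpha, beta, sensation), and 6 if neither pair is split. The Study Design list gives 7 with both pairs split and 6 with EEG counted once. Its seven are the eight without MEP.
- Outcomes: gait velocity plus five secondary outcomes.
- Correlation between test statistics: not in the documents. Assumed, and varied from 0 to 0.9.

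**The plan's own figure.** The power analysis states 79% power for Aim 2 at an effect of 28% with 40 per arm.

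- Weekly slope difference = 0.28 × 0.25 / 4 = 0.0175.
- SD of a participant's slope = √(0.16 × (1 − 0.95) / 10) = 0.0283, where 10 is the sum of squared deviations of times 0 to 4 from their mean.
- Standard error = 0.0283 × √(2/40) = 0.00632; ratio = 0.0175 / 0.00632 = 2.77.
- Power ≈ Φ(2.77 − 1.96) = 79%.

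So 79% reproduces as one two-group slope comparison at two-sided 0.05. It makes no allowance for more than one test. Whether that calculation suits a three-way interaction is a separate question, and nothing below rests on it.

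**Gait velocity, no feature truly modifying response.** For k independent tests, P(at least one false feature) = 1 − 0.95^k:

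- k = 1: 5.0%
- k = 6: 26.5%
- k = 7: 30.2%
- k = 8: 33.7%

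For correlated tests, equicorrelated normal statistics were simulated (400,000 runs, cut-off ±1.96):

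| Assumed correlation | 6 features | 7 features | 8 features |
|---|---|---|---|
| 0.3 | 24.1% | 27.2% | 30.0% |
| 0.5 | 20.7% | 23.0% | 24.9% |
| 0.7 | 16.5% | 17.8% | 19.2% |
| 0.9 | 10.9% | 11.4% | 12.0% |

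**Check by regression.** Participants' slopes were regressed on group, feature and their product, one feature at a time, with eight features, two of them binary (3,000 runs). At feature correlations 0, 0.3 and 0.5, at least one false feature arose in 32%, 31% and 27% with 80 participants. With 62, the number randomised in Aim 1 per the Progress Report, the figures were 34%, 30% and 26%. Each single test kept close to its level (4.8% to 5.2%), so the excess comes from the number of tests.

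**Secondary outcomes.** At most 8 × 6 = 48 tests, with 48 × 0.05 = 2.4 expected false positives. The chance of at least one is 91.5% if all are independent, and 63% at assumed correlations of 0.5 between features and 0.7 between outcomes.

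**After the change.** The TA MEP test has 5% error. Holm over the other seven starts at 0.05/7 = 0.0071; if independent, the chance of any false feature among them is 1 − (1 − 0.05/7)^7 = 4.9%. The two families together carry at most 5% + 5% = 10%.

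**The case against.** The best defence is that one primary test can be read from the plan: the power analysis names TA MEP, the Aim 2 text names gait velocity, and that pair has 5% error. The modifiers are pre-specified with hypotheses drawn from preliminary work, and Study Design describes Aim 2 as a subgroup analysis of a phase 2 trial. For such work an exploratory label may be enough, and Holm is a choice rather than a necessity. Correlation may also be high for some pairs, such as AROM with torque or alpha with beta, which lowers the figures.

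Most of this stands, and it sets the limits of the point. It does not remove it. The label sits in the sample-size reasoning, the analysis text gives it no effect, and the operational feature list leaves MEP out. Nor does the plan treat Aim 2 as a by-product: it carries its own hypothesis, and the power analysis says that the total was raised for it, from 30 to 40 per arm. Even with TA MEP protected, seven other features remain without a rule.

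A reader might go further and infer that the plan commits to 48 equal tests at 0.05, that any significant one identifies a feature, and that false features therefore appear in 25% to 34% of such trials. The documents do not support that. They give no decision rule and state 0.05 only for the power analysis. The counts of 8 and 48 depend on splitting two pairs, and the 25% end depends on an assumed correlation of 0.5.

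**Conclusion.** The point holds in a limited form. The plan has no error control for the Aim 2 interaction tests and does not carry its primary modifier into the analysis. If TA MEP on gait velocity is primary, that test is sound at 5%, but the other seven features on gait velocity carry about 30% (independent), 23% (correlation 0.5) or 18% (correlation 0.7). If all eight count equally, the figures are 34%, 25% and 19%.

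These figures assume that no feature modifies response, that each test is run two-sided at 0.05, and that the pairs are split as described. The correlations are assumptions; at 0.9 the figures fall to 11% and 12%. None of the counts and correlations examined brings the error down to 5%. The effect is confined to Aim 2.

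**What to change.** In the Aim 2 paragraph of Statistical Considerations:

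1. Name TA MEP on gait velocity as the single Aim 2 test at 0.05. Analyse it in the participants with MEP data, and report how many lack it, including those ineligible for TMS under the exclusion criteria.
2. Add MEP to the Aim 2 feature list under Study Design, so that the list agrees with the hypothesis and the power analysis. List every feature once, stating whether AROM and torque, and alpha and beta, are separate.
3. Test the remaining features on gait velocity with Holm adjustment, or report them as exploratory with no claim that a feature has been identified.
4. Report interactions for the five secondary outcomes as estimates with confidence intervals, without significance claims.

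This is a cheap improvement: wording only, with no new data and no change to Aim 1. The Progress Report places data analysis in the next approval period, so the wording can be settled before that analysis is run. The cost is lower power for each non-primary feature. The primary test will also rest on a subset whose size the documents do not give.
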